7.3.5 Questionnaires

Mood, quality of life, and sexual function will be assessed at baseline and at the end of the study visit. Quality of life and mood will be assessed by the PHQ-9⁸³ and Short Form 12 (SF-12).⁸⁴ Female sexual function will be assessed by the Female Sexual Function Inventory (FSFI) along with the Female Sexual Distress Scale (FSDS).⁸⁵ This measure is considered the “gold standard” paper and pencil assessments of sexual function and has excellent psychometric properties.⁸⁵ Male sexual response will be assessed by the International Index of Erectile Function (IIEF), a multidimensional scale for assessment of erectile dysfunction. The measure addresses the relevant domains of male sexual function (erectile function, orgasmic function, sexual desire, intercourse satisfaction, and overall satisfaction).⁸⁶ We will assess hypogonadal symptoms with the Androgen Deficiency and the Aging Male quantitative (qADAM) questionnaire and psychosexual function with the Psychosexual Daily Questionnaire (PDQ). We will assess quality of life relating to infertility and treatment with the FertiQoL survey.⁸⁷ There may also be some impact on fertility and we will investigate this in our study. We will use two simple scales to evaluate sleep, the STOP BANG questionnaire for sleep apnea,⁸⁸ and the Epworth Sleepiness Scale.⁸⁹ The Automated Self-Administered 24-hour Recall (ASA24) and Diet History Questionnaire II (DHQ II) will be used to assess past and current dietary intake. Male sunscreen exposure will be assessed by the Sun Exposure and Behaviour Inventory (SEBI v2).

8 Management of Adverse Experiences

8.1 Expected Adverse Experiences

All medications hold the possibility of an allergic reaction.

8.1.1 Phase I

There are no known side effects from meal replacements, except perhaps increased hunger. Orlistat is associated with gastrointestinal symptoms, most commonly flatulence, steatorrhea, and diarrhea. Prenatal vitamins may be associated with nausea or constipation (especially if they include iron). Increased physical activity may be associated with musculoskeletal pain. Pregnancy during Phase I is not an adverse event.

8.1.2 Phase II

The expected side effects with clomiphene include hot flashes, nausea, abdominal/pelvic pain and bloating, and mood changes. Rarely visual changes are noted. hCG given parenterally is associated with the risks of an intramuscular injection including pain at the injection site, bleeding, and infection. Intrauterine insemination is associated with the risk of pain and cramping after the procedure, spotting and less frequently bleeding and rarely pelvic infection. Both clomiphene and hCG alone and in combination are associated with an increased risk of multiple pregnancy. In the AMIGOS trial the rate of multiple pregnancy after conception was 7.6%.

8.1.3 Expected Serious Adverse Events

We do not anticipate serious adverse events during the first phase of this trial with lifestyle modification. These are more likely during the second and third phases of the trial. The expected serious adverse events are likely related to ovarian cyst formation which can result in hospitalization or surgery. Pregnancy and especially multiple pregnancy may also be a source of ectopic pregnancy, prematurity and maternal complications such as pre-eclampsia or eclampsia requiring hospital admission and induction of labor. None of the drugs or interventions are associated with increased risk of congenital anomalies.

9 Criteria for Modification or Discontinuation of Study Interventions

9.1 Phase I

There are no predetermined criteria for discontinuation during Phase I. Subjects will be allowed to continue in the trial even if they do not achieve the goals of the two interventions and eventually receive the infertility treatment in Phase II. However each subject will have to complete the 16 week pretreatment period before receiving the Phase II treatments. Subjects can not be accelerated into Phase II.

9.1.1 Intensive Lifestyle Modification

Orlistat intolerance: Subjects who are unable to tolerate the dose of orlistat will be allowed to skip doses at specific mealtimes to ease symptoms or to discontinue altogether with continued intolerance based on the decision of the site PI.

Algorithm for poor responders: Subjects who fail to lose appropriate weight in the intensive lifestyle modification group or fail to meet physical activity goals in either group will be contacted by the study coordinator on a weekly basis to review reasons. We will pilot smart phone automated responses also within this trial. Drs. [name] and [name] will lead the training (prior to the start of the study) and supervision (through monthly conference calls) of the interventions as well as review on a weekly basis of persistent poor responders and excessive responders (see below).

Algorithm for excessive responders: Excessive and rapid weight loss can be associated with health risks including formation of gall stones, development of hypotension, loss of energy, but rarely by an attack of gout. Subjects will be counseled at the onset about these health risks and to avoid excessive weight loss. Excessive response will be defined as a weight loss exceeding an average of 2.5 pounds per week or 10 pounds in a 4 week period. Subjects who exceed this at a monthly visit will be counseled to increase their caloric intake, by approximately 300-500 kcal/d, to slow the weight loss to our prescribed limits. We will follow subjects with their weekly weights collected by their Fitbit Aria wireless scales, and discuss them at both monthly investigator conferences and weekly coordinator conferences until they meet our guidelines. We will monitor the Fitbit steps during the first month of the study online to ensure that subjects do not exceed our guidelines of increasing 500 steps a day. We will also review monthly Fitbit records to ensure that subjects do not exceed the 10,000 steps on a regular basis. Subjects who consistently exceed our guidelines (more than 7 days in a 28 day period) will be advised to lower their activity to meet guidelines, and this will become a topic for weekly study coordinator and monthly investigator phone conferences

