1.5 Treatment

The intensive lifestyle modification intervention will consist of caloric restriction (consumption of approximately 1200-1500 kcal/d) centering around the use of meal replacements (Nutrisystem), use of an over-the-counter weight loss medication (Alli, which is brand name Orlistat, a gastric lipase inhibitor which limits gut fat absorption), and increased physical activity (goal of reaching 10,000 steps a day). The pretreatment intervention will last 16 weeks and is designed to promote a weight loss of approximately 7% of total body weight in the intensive group. Women in the standard lifestyle intervention (standard) will receive publicly available written materials that promote engagement in increased physical activity. Detailed instruction of physical activity will not be provided. Participants in both groups will receive activity tracking devices (Fitbit Wireless Activity Tracker) and wireless scales (Fitbit Aria Wireless Activity Scale) to promote adherence to the interventions and to allow monitoring for compliance by study personnel. The pretreatment intervention will last 16 weeks. Both groups will aim to build up to 10,000 steps/day with a recommendation to increase steps from baseline by 500 steps/per week. We will monitor subjects monthly during this preconception intervention. All subjects randomized will receive after 16 weeks of lifestyle modification, regardless of adherence or

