Increased Physical Activity Subjects will be asked to use the Fitbit Physical Activity Monitor during the screening phase to establish a mean number of steps over a 7 day period. This will then form the baseline number of steps. This baseline average of steps will be used as the starting point for increasing average steps a day by 500 steps a day per week until the desired maximum of 10,000 steps is reached. Subjects will be asked to maintain that level of physical activity throughout the study.

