9.1.2 Standard Lifestyle Intervention

Algorithm for poor responders: Subjects who fail to meet physical activity goals or who lose or gain excessive weight will be contacted by the study coordinator on a weekly basis to review reasons. We will pilot smart phone automated responses also within this trial. Drs. [name] and [name] will lead the training (prior to the start of the study) and supervision (through monthly conference calls) of the interventions as well as review of persistent poor responders.

Algorithm for excessive responders: We will monitor the FitBit steps during the first month of the study online to ensure that subjects do not exceed our guidelines of increasing 500 steps a

day. We will also review monthly Fitbit records to ensure that subjects do not exceed the 10,000 steps on a regular basis. Subjects who consistently exceed our guidelines (more than 7 days in a 28 day period) will be advised to lower their activity to meet guidelines, and this will become a topic for weekly study coordinator and monthly investigator phone conferences.

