10.2 Rationale for Design

Obesity is associated with subfertility through multiple mechanisms and lifestyle modification is frequently recommended as primary treatment before initiating infertility therapy. However this common sense recommendation is tempered by data that suggest that excessive or rapid weight loss as well as excessive physical activity may be associated with lower conception rates. We propose to focus on obtaining reproductive fitness through two types of lifestyle modification prior to infertility treatment. The first will be an intensive lifestyle modification designed to improve fitness through weight loss (with a dual approach of meal replacements combined with an anti-obesity medication) AND by increasing physical activity and the second arm will be a standard lifestyle modification which will focus on increasing physical activity alone. The meal replacements will be considered a prescribed medical treatment and will be dispensed and tracked to the intensive lifestyle intervention group throughout the pre-conception intervention. Both groups will be encouraged and monitored to achieve the same amount of physical activity. We hypothesize that weight loss as achieved by the more intensive intervention will be superior to the likely weight maintenance achieved with physical activity alone. However as noted in the background there are few data beyond our preliminary data to support that hypothesis. We do not have a control arm of no treatment as currently lifestyle modification is recommended universally for obese women.

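### The excessive-activity rule counts single days above 10,000 steps, so a woman who averages exactly the 10,000-step goal will usually be told to do less

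*Combined protocol and SAP*

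**What the plan says.** The goal is an average. Section 6.1 (Increased Physical Activity) starts from a 7-day baseline mean and proceeds by "increasing average steps a day by 500 steps a day per week until the desired maximum of 10,000 steps is reached". It adds: "Subjects will be asked to maintain that level of physical activity throughout the study". Section 1.5 gives the same goal for both arms: "Both groups will aim to build up to 10,000 steps/day".

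The rule for excess is a day count against the same number. Sections 9.1.1 and 9.1.2 use the same text: "We will also review monthly Fitbit records to ensure that subjects do not exceed the 10,000 steps on a regular basis", and women above guideline on "more than 7 days in a 28 day period) will be advised to lower their activity to meet guidelines". They also become an item for the weekly coordinator and monthly investigator calls. No section sets a tolerance above 10,000 steps or compares a woman's average with an upper limit.

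Three other statements bear on the point:

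- Section 10.2 gives a reason for a cap: "excessive or rapid weight loss as well as excessive physical activity may be associated with lower conception rates".
- The weight rule in 9.1.1 is written on a period average: "Excessive response will be defined as a weight loss exceeding an average of 2.5 pounds per week" (or 10 pounds in 4 weeks).
- Section 9.1 limits what can follow from a flag: "There are no predetermined criteria for discontinuation during Phase I".

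**The concern.** A limit on an average and a limit on single days are different things. Daily steps vary, so a woman whose average is 10,000 has days on both sides of it, and about half will be above. The rule allows 7 of 28, a quarter. A woman who does what 6.1 asks should therefore break the rule in 9.1.1 or 9.1.2 nearly every time it is applied.

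Two things are at stake. Activity is an intervention component in both arms, and women who meet the goal would be counselled to reduce it. And if nearly everyone at goal is flagged, the flag says little about who is truly exercising too much, which is the group that 10.2 worries about.

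The point applies to women at or near the plateau. It does not apply to those still well below 10,000 on the way up.

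**Working it through.** **Inputs from the documents.** Goal: an average of 10,000 steps a day (1.5, 6.1). Ceiling: 10,000 steps (9.1.1, 9.1.2). Flag: at least 8 of 28 days above the ceiling. Ramp: 500 steps a day per week. Phase I: 16 weeks. The documents state no flag rate, so there is no figure to reproduce. They also give no daily step SD, skew or correlation; those below are assumptions, shown as ranges.

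**1. Woman truly at goal.** Let p be the chance that one day exceeds 10,000. With days symmetric about a mean of 10,000, p = 0.5 for any SD. With independent days,

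P(flag) = 1 − BinomCDF(7; 28, 0.5) = 0.994.

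**2. Right-skewed days.** For lognormal days with mean 10,000, p = 1 − Φ(s/2), where s² = ln(1 + (SD/10,000)²).

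| Daily SD | p | P(flag), independent days |
|---|---|---|
| 1,000 | 0.480 | 0.989 |
| 2,000 | 0.461 | 0.981 |
| 3,000 | 0.442 | 0.970 |
| 4,000 | 0.424 | 0.955 |

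**3. Day-to-day correlation (simulated AR(1) days).**

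| Correlation | Symmetric, any SD | Lognormal, SD 2,000 to 4,000 |
|---|---|---|
| 0.3 | 0.978 | 0.95 to 0.91 |
| 0.5 | 0.950 | 0.91 to 0.87 |

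Wider assumptions lower the figure further: 0.84 with SD 5,000 and correlation 0.5, and 0.69 with SD 10,000 and correlation 0.5, the most extreme combination tried.

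**4. Women below goal** (symmetric, independent days; p = Φ((mean − 10,000)/SD)).

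| True mean | SD 1,000 | SD 2,000 | SD 3,000 |
|---|---|---|---|
| 9,500 | 0.67 | 0.93 | 0.96 |
| 9,000 | 0.06 | 0.67 | 0.87 |
| 8,000 | 0.00 | 0.06 | 0.41 |

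To bring the flag rate down to 5%, p must be about 0.15, which puts the true mean about 1.03 SD below the goal. At SD 2,500 that is about 7,400 steps.

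**5. Can the flag find over-exercisers?** A woman with a true mean of 12,000 is flagged in essentially 100% of windows (symmetric days, SD 1,000 to 3,000, correlation 0 to 0.5). Under the same assumptions a woman at goal is flagged in 95 to 99%. The two are hardly separated.

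**6. When it applies.** Weeks to plateau = (10,000 − baseline)/500. The baselines are assumed.

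| Baseline | Plateau reached | Full 28-day windows left in 16 weeks |
|---|---|---|
| 3,000 | week 14 | 0 |
| 4,000 | week 12 | 1 |
| 7,000 | week 6 | 2 |

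**7. Contrast with the weight rule.** The target is 7% over 16 weeks. At an assumed 90 kg this is 0.07 × 90 × 2.2046/16 = 0.87 lb per week, and at 120 kg it is 1.16. The limit of 2.5 lb per week is then 2.9 and 2.2 times target (2.7 times at 96 kg, the lifestyle-arm baseline mean in Table 4). For steps the ratio of limit to target is 1.0, and the scale changes from an average to single days.

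**The case against.** The strongest case is that the tight ceiling is intended and harmless. Section 6.1 words 10,000 as a maximum, and 1.5 states it simply as steps per day. Read as a daily ceiling, with 7 days in 28 allowed over it, the rule makes sense. Section 10.2 wants both arms at the same activity level so that weight loss is the contrast, and a ceiling close to the goal serves that. Staff can see each woman's step record, so the flag is only a screen. Few women may reach the plateau within Phase I, and the weight limit answers to acute health risks, so it need not share a ratio with the step limit.

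Much of this stands. The cap is deliberate, the number of women affected is unknown, and the consequence is small. The weight rule shows how an average-based limit can be written; it does not prove a defect by itself. The lower end of the flag probability also depends on the SD and correlation assumed.

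The daily-ceiling reading does not stand. In 6.1 the maximum is attached to average steps. If no day may exceed 10,000, one shorter day puts an average of 10,000 out of reach; a quarter of days as allowance is too little when about half fall above. That reading also collides with the poor-responder rule, which requires weekly contact with women who miss the activity goal. Equal activity is served just as well by a margin that applies to both arms. Finally, sorting women by hand on the calls is the work the rule was meant to do.

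**Conclusion.** The concern holds. Followed as written, the rule flags a woman who averages exactly the goal in 99.4% of 28-day windows with symmetric, independent days. It flags her in 87 to 99% across the assumed skew (SD up to 4,000) and correlation (up to 0.5), and in 69% in the most extreme case tried. The word 'usually' is therefore safe under every assumption used; the exact percentage is not known, because the documents give no daily step variability. Below the goal the result depends on that variability.

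The damage is operational. Adherent women at or near the plateau are advised to do less, call time is spent on them, and the flag loses its value for detecting excess. Both arms share the wording and 9.1 has no discontinuation criteria, so there is no direct bias to the primary comparison. The change should be made, but the trial's inference does not depend on it.

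**What to change.** Keep the cap. In 9.1.1 and 9.1.2, define excessive activity on the scale of the goal: a 28-day average above 10,000 by a margin that the sponsor sets. A day count against a daily ceiling set clearly above 10,000 would also work. The margin is needed: a limit on the average set at exactly 10,000 would still flag half of the women truly at goal.

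As an illustration, take a limit of 11,000 on the 28-day average, with daily SD 1,000 to 3,000:

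| True mean | Independent days | Correlation 0.5 |
|---|---|---|
| 10,000 (should not be flagged) | 0 to 4% | 0 to 15% |
| 12,000 (should be flagged) | 96 to 100% | 85 to 100% |

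The second row is one minus the first, because 11,000 lies midway between the two means. A wider margin lowers false flags and tolerates more drift above the common activity level, so the choice is clinical.

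The cost is one sentence in each of the two sections and the matching coordinator instruction. The tracker already supplies the data for a 28-day average.

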9.1.2 Standard Lifestyle Intervention

Algorithm for poor responders: Subjects who fail to meet physical activity goals or who lose or gain excessive weight will be contacted by the study coordinator on a weekly basis to review reasons. We will pilot smart phone automated responses also within this trial. Drs. [name] and [name] will lead the training (prior to the start of the study) and supervision (through monthly conference calls) of the interventions as well as review of persistent poor responders.

Algorithm for excessive responders: We will monitor the FitBit steps during the first month of the study online to ensure that subjects do not exceed our guidelines of increasing 500 steps a

day. We will also review monthly Fitbit records to ensure that subjects do not exceed the 10,000 steps on a regular basis. Subjects who consistently exceed our guidelines (more than 7 days in a 28 day period) will be advised to lower their activity to meet guidelines, and this will become a topic for weekly study coordinator and monthly investigator phone conferences.

9.2 Phase II

Criteria for altering the clomiphene dose and withholding hCG are noted above in description of the visits. Additionally a change in visual symptoms determined by the site investigator to be caused by clomiphene administration should be considered as a reason for discontinuing further challenge with clomiphene.

9.3 Phase III and IV

There are no study interventions during this part of the study.

10 Statistical Considerations

10.1 General Design Issues

This will be a randomized open label clinical trial of two types of lifestyle modification: one intensive focusing on weight loss through caloric restriction and anti-obesity medication, and the other less intensive (“standard”) focused on increasing physical activity for 16 weeks followed by three cycles of empiric ovarian stimulation combined with intrauterine insemination in obese women with unexplained infertility. We will track all pregnancies to completion. Subjects will be randomized 1:1 to the two treatments and stratified by site.

10.2 Rationale for Design

Obesity is associated with subfertility through multiple mechanisms and lifestyle modification is frequently recommended as primary treatment before initiating infertility therapy. However this common sense recommendation is tempered by data that suggest that excessive or rapid weight loss as well as excessive physical activity may be associated with lower conception rates. We propose to focus on obtaining reproductive fitness through two types of lifestyle modification prior to infertility treatment. The first will be an intensive lifestyle modification designed to improve fitness through weight loss (with a dual approach of meal replacements combined with an anti-obesity medication) AND by increasing physical activity and the second arm will be a standard lifestyle modification which will focus on increasing physical activity alone. The meal replacements will be considered a prescribed medical treatment and will be dispensed and tracked to the intensive lifestyle intervention group throughout the pre-conception intervention. Both groups will be encouraged and monitored to achieve the same amount of physical activity. We hypothesize that weight loss as achieved by the more intensive intervention will be superior to the likely weight maintenance achieved with physical activity alone. However as noted in the background there are few data beyond our preliminary data to support that hypothesis. We do not have a control arm of no treatment as currently lifestyle modification is recommended universally for obese women.

10.3 Outcomes

10.3.1 Primary Outcome Measurements

The primary outcome for this trial is the cumulative good birth outcome defined as a singleton or twin infant born at ≥ 37 weeks between 2500 and 4000g without a major congenital anomaly.

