1.2 Hypothesis

An intensive lifestyle modification intervention (which includes caloric restriction, use of an over-the-counter weight loss medication, and increased physical activity) designed to promote a weight loss of approximately 7% of initial body weight is more likely to achieve a good perinatal outcome (i.e. a healthy term normal weight infant) than a recommendation to standard lifestyle modification with increased physical activity (based on publicly available activity recommendations) in obese women with unexplained infertility.

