1.6 Primary efficacy parameter

Cumulative Good Birth Outcome during the study. Good Birth Outcome will be defined as a live birth of an infant born at ≥ 37 weeks, with a birth weight between 2500 and 4000g and without a major congenital anomaly.

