3.5 Good Birth Outcome

In this protocol we propose to narrow the primary outcome of a RMN trial from live birth, traditionally defined as any delivery beyond 20 weeks to one that reflects the desires of our patients and the demands of public health, i.e. a good perinatal outcome and specifically a good birth outcome. A sole focus on live birth as the metric of ART success in the U.S. has led to practices which encourage multiple embryo transfer to ensure high live birth rates, at the cost of an unacceptably high multiple pregnancy rate and among the multiple births a higher risk of adverse maternal (gestational hypertension, pre-eclampsia, gestational diabetes, cesarean delivery and hospital admission and neonatal (low birth weight, prematurity, NICU admission, birth defects) outcomes.^{71,72} A recent study of the National ART Surveillance Group at the CDC defined a “good perinatal outcome” as “a singleton or twin term live birth with normal birth weight neonates”.⁷³

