When “good perinatal outcome” was substituted for live birth, transfer of one embryo significantly improved the chance for this compared to multiple embryo transfers in women < 35 years old as well as women 35-37 years old. It is estimated that in the U.S. in 2011 a total of 36% of twin births and 77% of triplet and higher-order births resulted from conception assisted by fertility treatments.⁷⁵ Most of the twin births are thought to be due to ovarian stimulation and not IVF, and the rate of twin births in the U.S. has continued to increase over recent years, despite the dramatic reduction in triplet and other high order pregnancies (related to fewer embryos transferred during IVF).⁷⁵ We believe that the goals of any infertility treatment, either ovarian stimulation or IVF should be preferably a pregnancy with a good perinatal outcome.⁷⁵ We note a similar pattern with ovarian stimulation.⁷⁴ Gonadotropins for couples with unexplained infertility has a significantly higher live birth rate, but due to the high multiple rate, a lower proportion of good perinatal outcomes. In this study we have chosen a good perinatal outcome, revised here to exclude LGA babies (birth weight \geq 4500g) as they pose a significantly greater risk for poor perinatal outcomes due to macrosomia such as operative delivery, perineal trauma, shoulder dystocia, fetal injury, NICU admissions etc., especially in obese mothers. Because we are focusing on livebirth, we have altered the name from “good perinatal outcome” to “good birth outcome” in our protocol. Good birth outcome is also a term more comprehensible to our target patient population.

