3.7 Summary of AMIGOS data

The AMIGOS data provides reassurance that clomiphene/IUI is an effective empiric infertility treatment and is non-inferior to letrozole (and trending better in terms of live birth and a healthy live birth).

Table 6: Live birth per treatment cycles of AMIGOS patients with BMI \geq 30

Variable	Clomiphene group (N=70)	Letrozole group (N=90)	Gonadotropin group (N=81)	All (N=241)
		no./total no. (%)		
Live birth per treatment cycle				
Treatment cycle 1				
Total live birth	4/70(5.7)	9/90(10.0)	16/81(19.8)	29/241(12.0)
Live birth with EGA \geq 37 wks and 2500 \leq birth weight \leq 4000 g	3/70(4.3)	6/90(6.7)	10/81(12.4)	19/241(7.9)
Treatment cycle 2				
Total live birth	7/66(10.6)	5/81(6.2)	4/65(6.2)	16/212(7.6)
Live birth with EGA \geq 37 wks and 2500 \leq birth weight \leq 4000 g	6/66(9.1)	3/81(3.7)	3/65(4.6)	12/212(5.7)
Treatment cycle 3				
Total live birth	3/59(5.1)	1/76(1.3)	4/61(6.6)	8/196(4.1)
Live birth with EGA \geq 37 wks and 2500 \leq birth weight \leq 4000 g	3/59(5.1)	0/76(0)	3/61(4.9)	6/196(3.1)
Cumulative Live Birth Rate after 3 cycles				
Total live birth	14/70(20.0)	15/90(16.6)	24/81(29.6)	53/241(22.0)
Live birth with EGA \geq 37 wks and 2500 \leq birth weight \leq 4000 g	12/70(17.1)	9/90(10.0)	16/81(19.8)	37/241(15.4)

Implications for the FIT-PLESE Protocol

Changes in the proposed FIT-PLESE protocol from the OWL PCOS I Protocol – We propose changes to lower participant burden in terms of time and visits, ease the conduct of the trial for the RMN and RMN sites, and lower the overall cost of the trial. (NOTE: We have conducted the RO1 OWL PCOS trial with direct costs < \$500,000 per year, i.e. within the limits of an RO1 grant, most of which goes toward salary support that would be covered by the infrastructure support of the RMN grant).

First we propose to modify the primary outcome from live birth, to a good birth outcome (GBO) which we will define as: Singleton or twin infant (s) born at ≥ 37 weeks between 2500 and 4000g without a major congenital anomaly. We are modifying this to meet both our patient's and public health expectation to produce healthy infants. No one considers a 24 week, 400g premature infant who dies 1 day after delivery an optimal outcome. This is an emerging concept in infertility treatment recently used to examine the outcomes from single embryo transfers in the SART database.⁷⁴

[figure not shown]

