10.4 Sample Size and Accruals

10.4.1 Sample Size and Power Calculations

Estimates used for the power calculation are based on our experience from the OWL PCOS and AMIGOS trials as provided in the preliminary data section. The primary outcome for this trial is a good birth outcome defined as an infant (singleton or twin) born at ≥ 37 weeks between 2500 and 4000g without a major congenital anomaly. We will examine the cumulative rates between groups. We anticipate the proportion of good birth outcomes to be 0.25 in the standard lifestyle intervention (physical activity and weight maintenance) arm and 0.40 in the Intensive lifestyle modification arm. We anticipate that there will be an increased proportion of good birth outcomes in each group beyond our preliminary data, as we will not actively prevent pregnancy during the lifestyle intervention; therefore, they will have an additional 16 weeks to conceive prior to initiating empiric treatment. A sample size of 190 per treatment arm will provide 80% power to detect a 0.15 absolute difference in the proportion of good perinatal births (0.25 in the standard lifestyle modification and 0.40 in the intensive group using a two-sided test having a significance level of 0.05. Although the randomization is stratified by two factors (recruitment site and BMI status), this factor was not taken into consideration for the power analysis to be conservative because accounting for the correlation of these covariates with the outcome would simply increase the precision, and hence, increase the power. The sample size has been inflated to a total of 380 participants to allow for a dropout rate of 20%. We believe this 20% dropout rate is a reasonable estimate based on current experience in our PPCOS I, PPCOS II, OWL PCOS, and AMIGOS trials. The table below summarizes other possible sample size scenarios having a 0.15 absolute difference in the proportion of good birth outcomes between the two treatment arms, all of which we would have excellent power to detect (**Table 11**).

Table 11: Sample size scenarios based on varying assumptions

Standard Lifestyle Modification: Physical Activity Arm having a Good Birth Outcome	Intensive Lifestyle Modification Weight Loss and Physical Activity Arm: Proportion having a Good Birth Outcome		Significance Level (alpha)	Power (%)	N per Arm (0% Dropout)	N per Arm (20% Dropout)
0.15	0.30		0.05	80	121	152
			0.05	90	161	202
0.20	0.35		0.05	80	138	173
			0.05	90	185	232

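### Does the primary endpoint need a written rule for a term twin pair in which only one infant qualifies, and does the 4500 g figure in section 3.5 matter?

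*Combined protocol and SAP*

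**What the plan says.** The endpoint is stated in full in five places, all with a 37-week limit, a 2500 to 4000 g range and no major anomaly.

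- Section 1.6 requires "a live birth of an infant born at ≥ 37 weeks, with a birth weight between 2500 and 4000g" and section 1.8 repeats it. Both are singular and silent on twins.
- Section 3.7, under the implications for this protocol, has "Singleton or twin infant (s) born at ≥ 37 weeks between 2500 and 4000g without a major congenital anomaly".
- Section 10.3.1 has "a singleton or twin infant born at ≥ 37 weeks between 2500 and 4000g without a major congenital anomaly".
- Section 10.4.1 has "an infant (singleton or twin) born at ≥ 37 weeks between 2500 and 4000g without a major congenital anomaly".

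Section 1.2 only paraphrases the idea, as "a good perinatal outcome (i.e. a healthy term normal weight infant", with no gram or week limits.

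Section 3.5 gives the origin of the endpoint. It cites a surveillance definition, "a singleton or twin term live birth with normal birth weight neonates", and adopts it for this trial "revised here to exclude LGA babies (birth weight \geq 4500g". It then renames it good birth outcome. Table 6, which tabulates the earlier trial, uses 4000 g. Section 10.9 specifies a logistic regression on the woman's outcome, adjusted for site and baseline BMI, and adds no scoring rule for twins.

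**The concern.** Read literally, the singular wording in sections 10.3.1 and 10.4.1 is satisfied by one qualifying twin, whereas sections 3.5 and 3.7 lean towards all infants qualifying. A woman who delivers a term pair, one infant at 2600 g and the other at 2400 g, would be a success under the first reading and a failure under the second.

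This is the sole primary endpoint of an open-label trial. Ovarian stimulation makes twins foreseeable, and harm from multiple births is part of the reason section 3.5 gives for moving away from live birth. If the rule were chosen after outcomes were known by arm, a result close to the 5% boundary could in principle depend on it. The 4500 g in section 3.5 adds a second apparent conflict, this time in the weight ceiling itself.

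**Working it through.** **1. The plan's own figure.** Inputs from section 10.4.1: 0.25 v 0.40, two-sided alpha 0.05, power 80%, dropout 20%. With pooled variance under the null and no continuity correction,

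n = [1.960 × √(2 × 0.325 × 0.675) + 0.8416 × √(0.25 × 0.75 + 0.40 × 0.60)]² / 0.15² = (1.298 + 0.550)² / 0.0225 = 151.9, so 152 per arm.

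Then 152 / 0.8 = 190. Both match Table 11. Power is 80.0% at 152 per arm and 88.0% at 190.

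**2. How many women could be scored differently.** Let t be the twin share of good outcomes and d the proportion of those pairs with only one qualifying infant. Take t = 0.076, the multiple-pregnancy rate per conception in section 8.1.2. Take d = 0.25 to 0.50, which is assumed because the documents give no value.

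- Standard arm: 0.25 × 190 × 0.076 = 3.6 twin outcomes; × d = 0.9 to 1.8 women.
- Intensive arm: 0.40 × 190 × 0.076 = 5.8 twin outcomes; × d = 1.4 to 2.9 women.

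**3. Effect on power.** If 0.25 and 0.40 count one qualifying twin as a success, an all-infants rule multiplies both by (1 − t × d).

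| t × d | Rates | Difference | Power at 152 | Power at 190 |
|---|---|---|---|---|
| 0 | 0.2500 v 0.4000 | 15.0 points | 80.0% | 88.0% |
| 0.076 × 0.25 = 0.019 | 0.2453 v 0.3924 | 14.7 points | 78.9% | 87.1% |
| 0.076 × 0.50 = 0.038 | 0.2405 v 0.3848 | 14.4 points | 77.7% | 86.2% |

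If the planning rates already require all infants to qualify, nothing moves. The documents do not say which.

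**4. Why t = 0.076 is probably high.** It is a rate per conception, not per term birth. Section 8.1.2 does not say which arms of the earlier trial it covers; section 3.6 reports a high multiple rate with gonadotropins, which are not used here. Section 10.4.1 expects extra good outcomes from pregnancies conceived in the 16-week lifestyle phase, before any stimulation. Section 3.5 reports that a high multiple rate lowers the share of good outcomes, so multiples should be under-represented among them. With an assumed t of 0.02 to 0.04 and the same d, t × d runs from 0.005 to 0.02, and power at 152 is 79.7% to 78.8%.

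**5. Could a conclusion flip?** Unadjusted chi-square without continuity correction, 190 per arm:

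| Good outcomes, standard v intensive | p |
|---|---|
| 47 v 65 (near the boundary) | 0.043 |
| 46 v 64 (one rescored in each arm) | 0.042 |
| 45 v 63 (two rescored in each arm) | 0.041 |
| 46 v 63 (one and two rescored) | 0.054 |
| 48 v 76 (about the planned effect) | 0.002 |
| 46 v 73 (two and three rescored) | 0.003 |

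Only an unequal split, starting from a result already at the boundary, crosses 0.05.

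**6. The weight ceiling.** Sections 1.6, 1.8, 3.7, 10.3.1, 10.4.1 and Table 6 all use 4000 g. Section 3.5, a background section, is the only place with 4500 g.

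**The case for a change.** The strongest case for a change is that the rule is not written anywhere, and that the statistical section, which governs the analysis, uses the wording most open to a one-twin reading. The plural forms that suggest otherwise sit in background text. The trial is open label, and the DSMB charter lists a primary-outcome update in every report, so a rule is needed during conduct and not only at the end. One sentence would settle it, and the infant hospital records needed to apply it are already collected under section 7.2.

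The factual part of this stands: the rule has to be inferred. The inference is not difficult, though. Section 3.5 names the one way it revises the cited definition, which is to exclude large infants, and mentions no change to how twins count. Gestational age and birth weight come from hospital records, so the open-label design gives little room for biased scoring. Writing the rule down would also leave the sponsor free to choose either version, and the comparison is valid under both.

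On weight, a ceiling of 4500 g would not be trivial if it were actually applied, because a weight-loss programme could shift the 4000 to 4500 g share differently by arm. If good outcomes rose by an assumed 15% in the standard arm and 5% in the intensive arm, the rates would be 0.2875 v 0.42 and power at 152 per arm about 68%. That shows that the ceiling matters in principle. It does not show that the plan is in doubt about it, since every statement an analyst would work from gives 4000 g.

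**Conclusion.** No change to the plan follows. The twin point is a missing detail that analysts can fill sensibly from sections 3.5 and 3.7 by requiring every infant of the pair to qualify. The 4500 g is a slip in background text; that it is a slip is an inference, but a strong one given the agreement of all the operative statements and Table 6.

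The effect is at most about 2 points of power at 152 per arm (80.0% to 77.7%) and one to three women per arm. That rests on an assumed 25-50% discordance, on a twin share of 7.6% that is probably too high, and on planning rates that count one qualifying twin as a success. Without the last condition, planned power is unchanged. The sample size stays at 190 per arm and the primary analysis is unaffected. The two wordings could be aligned if the text is being edited for another reason, but no result depends on it.
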